19.2 Appendix 2: Philips Sonicare ProtectiveClean® Instructions for use

Philips Sonicare ProtectiveClean® - ©2014 Koninklijke Philips Electronics NV (KPENV).

The Sonicare toothbrush complies with the safety standards for electromagnetic devices. If you have a pacemaker or other implanted device, contact your physician or the device manufacturer of the implanted device before you use the Sonicare.

Package Insert

General Description

IMPORTANT

Read this user manual carefully before you use the appliance and save it for future reference.

DANGER

-Keep the charging base away from water.

Do not place or store it over or near water contained in a bathtub, washbasin, sink etc. Do not immerse the charger in water or any other liquid. After cleaning, make sure the charger is completely dry before you connect it to the mains.

WARNING

-The mains cord cannot be replaced. If the mains cord is damaged, discard the charger.

- Always have the charger replaced with one of the original type in order to avoid a hazard.
- Do not use the charger outdoors or near heated surface.
- Check if the voltage indicated on the appliance corresponds to the local mains voltage before you connect the appliance.
- If the appliance is damaged in any way (brush head, toothbrush handle or charger), stop using it. This appliance contains no serviceable parts. If the appliance is damaged, contact the Consumer Care Centre in your country (see chapter 'Warranty and support').
- This appliance can be used by children and by persons with reduced physical, sensory or mental capabilities or lack of experience and knowledge if they have been given supervision or instruction concerning use of the appliance in a safe way and understand the hazards involved. Cleaning and user maintenance shall not be made by children without supervision.
- Children shall not play with the appliance.

CAUTION

- Do not clean the brush head, handle or the charger in the dishwasher.
- If you have had oral or gum surgery in the previous 2 months, consult your dentist before you use the toothbrush.
- Consult your dentist if excessive bleeding occurs after using this toothbrush or if bleeding continues to occur after 1 week of use. Also consult your dentist if you experience discomfort or pain when you use the Philips Sonicare.
- The Sonicare toothbrush complies with the safety standards for electromagnetic devices. If you have a pacemaker or other implanted device, contact your physician or the device manufacturer of the implanted device before to use.
- If you have medical concerns, consult your doctor before you use the Sonicare.
- This appliance has only been designed for cleaning teeth, gums and tongue. Do not use it for any other purpose. Stop using the appliance and contact your doctor if you experience any discomfort or pain.
- The Sonicare toothbrush is a personal care device and is not intended for use on multiple patients in a dental practice or institution.
- Stop using a brush head with crushed or bent bristles. Replace the brush head every 3 months or sooner if signs of wear appear. Do not use other brush heads than the ones recommended by the manufacturer.
- If your toothpaste contains peroxide, baking soda or bicarbonate (common in whitening toothpastes), thoroughly clean the brush head with soap and water after each use. This prevents possible cracking of the plastic.

Electromagnetic fields (EMF)

This Philips appliance complies with all applicable standards and regulations regarding exposure to electromagnetic fields.

Radio Equipment Directive

- Radio Equipment in this product operates at 13.56 MHz
- Maximum RF power transmitted by the Radio Equipment is 30.16dBm

Introduction

Congratulations on your purchase and welcome to Philips! To fully benefit from the support that Philips offers, register your product at www.philips.com/welcome.

Brush heads

Your Philips Sonicare comes with one or more brush heads which are designed to deliver superior results for your oral care needs.

Philips Sonicare BrushSync Technology

Your smart brush heads use a microchip to sync with your handle, enabling brush head replacement reminder. For more information regarding the brush head replacement reminder, see 'Features'. This symbol indicates the brush head is equipped with BrushSync technology. (Fig. 2)

Brushing modes

Your power toothbrush is equipped with clean mode.

Clean mode

Clean is a 2-minute mode. It gives you a thorough and complete clean and is recommended to be used with the C2 Optimal Plaque Control brush head.

Intensities

Your power toothbrush gives you the option to choose between low and high intensity.

Note: When you use the toothbrush for the first time, the default setting is the low intensity.

- Press the power button once to turn on the toothbrush.
- Press a second time **within 2 seconds** to change the intensity.
- Press a third time **within 2 seconds** to pause.

After 2 seconds of brushing, pressing the power button again will also pause the toothbrush.

Using your Philips Sonicare

Brushing instructions

1 Press the brush head onto the handle in such a way that the bristles will face the front of the handle. (Fig. 3)

2 Firmly press the brush head down onto the metal shaft until it stops.

Note: it is normal to see a slight gap between the brush head and the handle.

3 Wet the bristles. (Fig. 4)

4 Apply a small amount of toothpaste on the bristles. (Fig. 5)

5 Place the toothbrush bristles against the teeth at a slight angle (45 degrees), pressing firmly to make the bristles reach the gumline or slightly beneath the gumline. (Fig. 6) A change in vibration (and a slight change in sound) alerts you when you apply too much pressure while brushing.

Note: Keep the center of the brush in contact with the teeth at all times.

6 Press the power on/off button to turn on the Philips Sonicare. (Fig. 7)

7 Gently keep the bristles placed on the teeth and in the gumline. Brush your teeth with small back and forth motion so the bristles reach between the teeth. (Fig. 8)

Note: The bristles should slightly flare. Do not scrub.

8 To clean the inside surfaces of the front teeth, tilt the brush handle semi-upright and make several vertical overlapping brushing strokes on each tooth. (Fig. 9)

9 To make sure you brush evenly throughout the mouth, divide the mouth into 4 sections using the Quadpacer feature. (Fig. 10) The quadpacer feature beeps after 30 seconds.

10 Brush for the full 2 minutes following the Quadpacer. (Fig. 11) After 2 minutes, the toothbrush will automatically shut off.

–After you have completed the brushing cycle, you can spend additional time brushing the chewing surfaces of your teeth and areas where staining occurs. (Fig. 12)

Your Philips Sonicare toothbrush is safe to use on;

–Braces (brush heads wear out sooner when used on braces)

–Dental restorations (fillings, crowns, veneers)

Note: When the Philips Sonicare toothbrush is used in clinical studies, it must be used in the Clean mode (for plaque and gum health claims) with EasyStart turned off.

Features

–EasyStart

–Brush head replacement reminder

–Pressure sensor

–Quadpacer

EasyStart

This Philips Sonicare model comes with the EasyStart feature deactivated. The EasyStart feature gently increases the power over the first 14 brushings to help you get used to the brushing with the Philips Sonicare.

To activate EasyStart see 'Activating or deactivating features'.

Brush head replacement reminder

Your Philips Sonicare is equipped with BrushSync technology that tracks the wear of your brush head. (Fig. 13)

- 1 When attaching a new smart brush head for the first time the brush head replacement reminder light blinks green three times. This confirms you have a Philips brush head with BrushSync technology.
- 2 Over time, based on the pressure you apply and the amount of time used, the handle will track brush head wear in order to determine the optimal time to change your brush head. This feature gives you the guarantee for the best cleaning and care of your teeth.
- 3 When the brush head replacement reminder light lights up amber, you should replace your brush head.

To deactivate the brush head replacement reminder see 'Activating or deactivating features'.

Pressure sensor

Your Philips Sonicare is equipped with an advanced sensor that measures the pressure you apply while brushing. If you apply too much pressure, the toothbrush will provide immediate feedback to indicate that you need to reduce the pressure. This feedback is given by a change in vibration and therefore brushing sensation.

To deactivate the pressure sensor see 'Activating or deactivating features'.

Quadpacer

The Quadpacer is an interval timer that has a short beep and pause to remind you to brush the different sections of your mouth.

Depending on the brushing mode you have selected (see 'Brushing modes'), the Quadpacer beeps at different intervals during the brushing cycle.

Activating or deactivating features

You can activate or deactivate the following features of your toothbrush;

- EasyStart
- Brush head replacement reminder
- Pressure sensor

To activate or deactivate these features, follow the instructions below;

EasyStart

- 1 Put the handle on the plugged-in charger.
- 2 Press and hold the power on/off button while the handle remains on the charger.
- 3 Keep the power on/off button pressed until you hear a single short beep (after 2 seconds).
- 4 Release the power on/off button.

–Triple tone of how-med-high means the EasyStart feature has been activated. The brush head replacement light and battery light will also blink green 3 times in unison to confirm activation.

–Triple tone of high-med-how means the EasyStart feature has been deactivated. The brush head replacement light and battery light will also blink amber 3 times in unison to confirm deactivation.

Note: To achieve clinical efficacy, EasyStart needs to be deactivated.

Brush head replacement reminder

- 1 Put the handle on the plugged-in charger.
- 2 Press and hold the power on/off button while the handle remains on the charger.
- 3 Keep the power on/off button pressed until you hear a series of two short beeps (after 4–5 seconds).
- 4 Release the power on/off button.

- Triple tone of how–med–high means the Brush head replacement reminder feature has been activated. The brush head replacement light and battery light will also blink green 3 times in unison to confirm activation.
- Triple tone of high–med–low means the Brush head replacement reminder feature has been deactivated. The brush head replacement light and battery light will also blink amber 3 times in unison to confirm deactivation.

Pressure sensor

- 1 Put the handle on the plugged–in charger.
- 2 Press and hold the power on/off button while the handle remains on the charger.

3 Keep the power on/off button pressed until you hear a series of three short beeps (after 6–7 seconds).

- 4 Release the power on/off button.

–Triple tone of how–med–high means the pressure sensor feature has been activated. The brush head replacement light and battery light will also blink green 3 times in unison to confirm activation.

–Triple tone of high–med–low means the pressure sensor feature has been deactivated. The brush head replacement light and battery light will also blink amber 3 times in unison to confirm deactivation.

If you continue holding the power on/off button after the three short beeps, the activate/deactivate sequence repeats.

Battery status and charging

- 1 Put the pug of the charger in an electrical outlet.

- 2 Place the handle on the charger.

–The charger will emit 2 short beeps to confirm that the handle is placed properly.

–The flashing light of the battery level indicator shows that the toothbrush is charging.

–When handle is fully charged on the charger, the battery light shows solid green for 30 seconds and switches off.

Note: Your toothbrush comes pre–charged for first use. After first use, charge for at least 24 hours.

Battery status (when handle is not on charger)

When removing the Philips Sonicare from the charger, the battery light at the bottom of the toothbrush will indicate the status of the battery life.

–Solid green LED; full battery

–Flashing green LED; medium battery

–Flashing amber LED and three beeps; low battery

–Flashing amber LED and two sets of five beeps; No brushing sessions left (charge toothbrush).

Cleaning

Note: Do not clean the brush head, handle or travel case in the dishwasher.

Toothbrush handle

1 Remove the brush head and rinse the metal shaft area with warm water. Make sure you remove any residual toothpaste (Fig. 14).

Note: Do not push on the rubber seal on the metal shaft with sharp objects, as this may cause damage.

2 Wipe the entire surface of the handle with a damp cloth.

Note: Do not use isopropyl rubbing alcohol, vinegar or bleach to clean handle as this may cause discoloration.

Brush head

1 Rinse the brush head and bristles after each use (Fig. 15).

2 Remove the brush head from the handle and rinse the brush head connection with warm water at least once a week.

Charger

1 Unplug the charger before you clean it.

2 Wipe the surface of the charger with a damp cloth.

Storage

If you are not going to use your Philips Sonicare for an extended period of time, unplug the charger from the wall socket, clean it and store it in a cool and dry place away from direct sunlight.

Locating the model number

Look on the bottom of the Philips Sonicare toothbrush handle for the model number (HX681x).

Recycling

–This symbol means that this product shall not be disposed of with normal household waste (2012/19/EU) (Fig. 24).

–This symbol means that this product contains a built-in rechargeable battery which shall not be disposed of with normal household waste (Fig. 25) (2006/66/EC). Please take your product to an official collection point or a Philips service center to have a professional remove the rechargeable battery.

–Follow your country's rules for the separate collection of electrical and electronic products and rechargeable batteries. Correct disposal helps prevent negative consequences for the environment and human health.

Removing the rechargeable battery

Warning: Only remove the rechargeable battery when you discard the appliance. Make sure the battery is completely empty when you remove it.

To remove the rechargeable battery, you need a towel or cloth, a hammer and a flat-head (standard) screwdriver. Observe basic safety precautions when you follow the procedure outlined below. Be sure to protect your eyes, hands, fingers, and the surface on which you work.

1 To deplete the rechargeable battery of any charge, remove the handle from the charger, turn on the Philips Sonicare and let it run until it stops. Repeat this step until you can no longer turn on the Philips Sonicare.

2 Remove and discard the brush head. Cover the entire handle with a towel or cloth (Fig. 16).

3 Hold the top of the handle with one hand and strike the handle housing 0.5 inch above the bottom end. Strike firmly with a hammer on all 4 sides to eject the end cap (Fig. 17).

Caution: Be aware of the sharp edges of the battery tabs so as to avoid injury to your fingers.

4 Remove the end cap from the toothbrush handle. If the end cap does not release easily from the housing, repeat step 3 until the end cap is released (Fig. 18).

5 Holding the handle upside down, press the shaft down on a hard surface. If the internal components do not easily release from the housing, repeat step 3 until the internal components are released (Fig. 19).

6 Remove the rubber battery cover.

7 Wedge the screwdriver between the battery and the black frame at the bottom of the internal components. Then pry the screwdriver away from the battery to break the bottom of the black frame (Fig. 20).

8 Insert the screwdriver between the bottom of the battery and the black frame to break the metal tab connecting the battery to the green printed circuit board. This will release the bottom end of the battery from the frame (Fig. 21).

9 Grab the battery and pull it away from the internal components to break the second metal battery tab (Fig. 22).

Caution: Be aware of the sharp edges of the battery tabs so as to avoid injury to your fingers.

10 Cover the battery contacts with tape to prevent any electrical short from residual battery charge. The rechargeable battery can now be recycled and the rest of the product discarded appropriately (Fig. 23).

[figure not shown]
Warranty and support

If you need information or support, please visit
www.philips.com/support or read the international warranty leaflet.

Warranty restrictions

The terms of the international warranty do not cover the following;

- Brush heads.
- Damage caused by use of unauthorized replacement parts.
- Damage caused by misuse, abuse, neglect, alterations or unauthorized repair.
- Normal wear and tear, including chips, scratches, abrasions, discoloration or fading.

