4 INTRODUCTION

4.1 Background and rationale

Gingival recession is defined as the apical shift of the gingival margin with respect to the cemento-enamel junction it is associated with attachment loss and with exposure of the root surface to the oral environment (Cortellini and Bissada, 2018). The etiology of gingival recessions remains unclear. Among predisposing factors tooth brushing has been suggested. A few systematic reviews support or refute the association between tooth brushing and gingival recession. In one systematic review, among the 18 examined studies, one concluded that the toothbrushes significantly reduced recessions on facial tooth surfaces over 18 months, two concluded that there appeared to be no relationship between tooth brushing frequency and gingival recession, while eight studies reported a positive association between tooth brushing frequency and recession. Several studies reported potential risk factors like duration of tooth brushing, brushing force, frequency of changing the tooth-brushing technique (Cortellini and Bissada, 2018).

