Philips Sonicare brush heads work with sonic technology: High-speed vibrations in the toothbrush handle power up to 62,000 brush movements per minute that whip up the toothpaste into gentle cleaning bubbles, driving them deep between the teeth and the gum for additional cleaning. The sonic toothbrush Philips Sonicare ProtectiveClean has an intuitive pressure sensor that helps patients to guide their brushing technique. One of the advantages of using this toothbrush is that pressure sensor provides real-time feedback so patient will adopt a softer touch to protect teeth and gums. This toothbrush works on 2 modes to remove plaque gently and effectively. On some Philips Sonicare sonic brushes, a program named "Gum Care" also adds an extra minute of reduced-power brushing to gently massage the gums, improving gum health. In addition, the BrushSync feature tracks brush head effectiveness based on brushing time and pressure and alerts patients when it is time for replacement.

The toothbrush head Philips Sonicare Optimal Plaque Defense possesses densely-packed, high-quality bristles that remove up to 7x more plaque than a manual toothbrush (Philips Oral Healthcare, unpublished data). This brush head works with a sonic technology, high-speed vibrations in the toothbrush handle power up to 62,000 brush movements per minute that whip up the toothpaste into gentle cleaning bubbles, driving them deep between the teeth and the gum for cleaning. Philips Sonicare ProtectiveClean has an intuitive pressure sensor that helps patients to guide their brushing technique. This pressure sensor provides a real-time feedback, thus encouraging the subject to adopt a softer touch in order to protect his/her teeth and gums. This feature is one of the benefits of using this toothbrush. This toothbrush works on 2 modes to remove plaque gently and effectively. The Gum Care mode also adds an extra minute of reduced -power brushing to gently massage the gums, improving gum health

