5.1.2 Primary endpoint

Evaluation of the gingival abrasion (GA): Macro-relief scoring.

A first method for the evaluation of gingival abrasion (GA) will consist in a method of macro-relief scoring of gingival tissue as described previously by Perin *et al.* with skin tissue. This evaluation consists of acquiring macroscopic views of each investigated surface and then classifying them by observers according to a reference groups of defined abrasion intensity. This evaluation scoring,

using photo grading technique, allow delayed and blinded scoring, independent of whole-subject appearance, thus decreasing subjectivity (Perin et al., 2000).

The macro-relief gingival abrasion scoring technique consists of acquiring macroscopic photographs of each gingival quadrant at each time point. Observers will score these photographs in a double-blind manner by comparing the different photographs with a photonumerical reference scale used as standard. This scale, composed of 5 criteria each scored from 0 to 3, has already been retained by observers as being representative of the different grades of gingival abrasion. The final score will range from 0 (no abrasion) to 15 (severe gingival abrasion).

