6.3 Treatment groups

The choice of the tooth brushing instrumentation and the brush group will be done randomly by one operator. In addition, these groups will be selected for brushing with or without instructions of the operator with manual or electric toothbrush. The Examiner will be blind and, at any stage of the measurements not informed of the distribution / repartition of the brush group / selected devices.

- ✓ Brush group 1: Sonicare ProtectiveClean® toothbrush (HX6848/92 Philips) equipped with a C2 Optimal Plaque Defense head (HX9022/10 Philips) + oral hygiene instructions + Manufacturer's instructions + sodium monofluorophosphate (1450 ppm F) toothpaste (elmex® SENSITIVE PROFESSIONAL Colgate-Palmolive) with a low degree of abrasivity.
- ✓ Brush group 2: Inava® 20/100 (Code ACL: 3401561130767) manual toothbrush + oral hygiene instructions + Manufacturer's instructions + sodium monofluorophosphate (1450 ppm F) toothpaste (elmex® SENSITIVE PROFESSIONAL Colgate-Palmolive) with a low degree of abrasivity (= 79).

1st Group: Electric toothbrush + manufacturer's instructions + professional recommendations + sodium monofluorophosphate (1450 ppm F) toothpaste (elmex® SENSITIVE PROFESSIONAL)
2th Group: Manual toothbrush + manufacturer's instructions + professional recommendations + sodium monofluorophosphate (1450 ppm F) toothpaste (elmex® SENSITIVE PROFESSIONAL)

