6.6 Time and repartition of tooth brushing procedures

The randomization of the toothbrush and the brush group will be performed as previously described by the operator (see section 6.4). Subjects will receive a Sonicare ProtectiveClean® toothbrush (HX6848/92 Philips) equipped with a C2 Optimal Plaque Defense head (HX9022/10 Philips) or a standard manual toothbrush (Pierre Fabre Inava® 20/100) and a sodium monofluorophosphate (1450 ppm F) toothpaste (elmex® SENSITIVE PROFESSIONAL). The brushing duration will be inconspicuously measured in seconds with a stopwatch, while the participants are brushing. The mean duration of brushing will be 30 seconds per quadrant for manual or power brushers. All participants with their assigned toothbrush (being either the Philips Sonicare ProtectiveClean® 6809/04 or Inava® 20/100) will brush with manufacturers / professional recommendations. They will use a sodium monofluorophosphate (1450 ppm F) toothpaste. At the beginning of the study three and/or four 75 ml tubes of toothpaste will be given to each patient. It has been calculated that the dose of toothpaste per brushing was 1.21 g on average i.e. 217.8 grams for 90 days (Precisa®100C-3000D). The tubes of toothpaste are weighed at the beginning (average 108 g) and at the end of this study. It is thus possible to measure the global quantity of toothpaste used and the possible effect of this use on the surface texture of the gum tissue.

Thus, brushing time for the whole mouth will be 2 minutes for each patient from both toothbrush groups. The evaluation time and the consequences of brushing will be assessed immediately and 90 days later.

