8.3 Instructions for Use

The instructions for use of Philips Sonicare ProtectiveClean® and Pierre Fabre Inava® are provided in the products notices (see appendices in sections 19.2 and 19.3). The investigators will give the patients the following oral hygiene instructions:

Place the bristles against the teeth at a 45° angle, towards the gum line and start brushing. Depending on the allocation group the following instructions will be given:

Electric toothbrush: Apply light pressure and move the brush head slowly horizontally without scrubbing across the teeth to brush all dental surfaces in a regular movement. It is not necessary to do any other movement. The ProtectiveClean Sonicare® brush will generate small vibrations every 30 seconds so the patient can adjust the pace of his movement to the global brushing time of 2 minutes.

Manual toothbrush: The “rolling” modified Bass technique should be used: the head of the brush must be rotated upwards on the lower teeth and downwards on the upper teeth towards the occlusal surface. The occlusal surfaces are cleaned using the scrub technique (the toothbrush is swept along the teeth backwards and forwards). In palatal/lingual sites a slight horizontal movement can be combined with a vertical translation as described above.

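### The sonic arm gets two unreconciled pressure instructions, light in section 8.3 and firm in step 5 of Appendix 2, and the protocol does not say which governs

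*Protocol*

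**What the plan says.** Section 8.3 (Instructions for Use) has the investigators tell patients in both arms to set the bristles at 45° towards the gum line. For the electric brush it continues: "Apply light pressure and move the brush head slowly horizontally without scrubbing across the teeth". The same section names the product leaflets in Appendices 2 and 3 as the instructions for use.

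Step 5 of the brushing instructions in Appendix 2, the sonic brush manual, also sets the bristles at 45°, and there the user is told to do so "pressing firmly to make the bristles reach the gumline or slightly beneath the gumline".

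Both texts apply to the test arm. Section 6.3 describes brush group 1 as the sonic toothbrush "equipped with a C2 Optimal Plaque Defense head (HX9022/10 Philips) + oral hygiene instructions + Manufacturer's instructions". Section 6.6 says that all participants "will brush with manufacturers / professional recommendations". No section ranks one set of instructions above the other.

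The primary endpoint in section 5.1.2 is "Evaluation of the gingival abrasion (GA): Macro-relief scoring". The table in section 11.5 shows that recession is one of its five criteria. On the causes of recession, section 4.1 says: "Several studies reported potential risk factors like duration of tooth brushing, brushing force". It also describes the brush's pressure sensor as "encouraging the subject to adopt a softer touch in order to protect his/her teeth and gums".

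**The concern.** The trial asks whether one brush abrades the gingiva less than another. How hard the patient presses is close to the mechanism being studied, and section 4.1 treats it so. A sonic-arm patient hears one pressure instruction at the clinic and can read a different one in the manual for the same placement of the same brush. If patients divide between the two, the test arm is not receiving one defined brushing technique. The report could then not say which technique its abrasion result describes.

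**Working it through.** The point rests on comparing texts. The protocol gives no figure for the effect of pressure on the score, so there is none to reproduce.

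1. **Same placement, different pressure.** Section 8.3: bristles at 45° towards the gum line, light pressure. Appendix 2, step 5: bristles at a slight angle of 45°, pressed firmly so that they reach the gumline or just below it. The angle and site match; the pressure does not.

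2. **Is step 5 only about placement?** It comes before the brush is switched on in step 6, which supports that reading. But the next sentence of step 5 describes the alert for too much pressure during brushing, so the step also reads as guidance on brushing pressure.

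3. **Rest of the manual.** Step 7, after switch-on, asks for the bristles to be kept gently in place, and its note warns against scrubbing. This agrees with section 8.3. The manual is therefore mixed, and the conflict lies in step 5.

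4. **Are both texts in force?** Section 6.3 joins the two sets of instructions with plus signs, section 6.6 names both, and section 8.3 points to the manual. Appendix 2 tells the user to read the manual and keep it. The synopsis says that technique is explained orally. The written text thus stays available to the patient, and no order of precedence is given.

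5. **Link to the endpoint.** There are five criteria scored 0 to 3, so the maximum is 5 × 3 = 15. Recession can contribute at most 3 of 15 points (3/15 = 20%). Section 4.1 names force as a potential risk factor for that component. It also accepts that the shear forces of brushing can injure the surface epithelium of the gingiva. Neither statement gives a size.

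6. **Exposure.** There are 30 patients in the sonic arm. Two brushings a day for 90 days make 2 × 90 = 180 per patient, which matches the toothpaste figures in section 6.6 (217.8 g / 1.21 g = 180). This counts exposure to the wording. It does not show that anyone's pressure changed.

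7. **Could the instruction followed be recovered afterwards?** The flow chart and sections 9.3 and 9.4 schedule patient-reported use, brush age, brush wear on a 0–4 scale and toothpaste weight. None of these measures pressure. Wear may reflect force loosely, but it also depends on time in use. The handle tracks pressure for its replacement reminder, but the protocol schedules no reading of it.

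**The case against.** The best defence is that the manual, read as a whole, asks for gentle brushing. The firm wording belongs to positioning, later steps call for gentle contact without scrubbing, and the sensor warns of excess pressure. Switching the sensor off takes a deliberate 6–7 second button hold on the charger, which no text asks patients to do. The investigator explains technique in person and the first brushing is supervised. Much of this stands, and it narrows the conflict. It does not remove it: the sensor signals only too much pressure, supervision covers one session, and step 5 remains at odds with section 8.3.

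A reader might infer four stronger things that the documents do not support.

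- **That the two texts are opposed throughout, movement included.** Section 8.3 says other movements are unnecessary; it does not forbid them. Slow horizontal movement without scrubbing is compatible with the manual's small back-and-forth motion. The manual's vertical strokes concern the inner surfaces of the front teeth, whereas section 5.1.1 records the primary variables on buccal aspects.
- **That the abrasion result can no longer be attributed to the test arm.** Section 6.3 defines each arm as a brush plus its instructions, and randomisation still supports comparing those packages. What suffers is the description of the technique.
- **That variability rises in the sonic arm only.** Section 8.3 gives the manual arm no pressure instruction at all, and Appendix 3 refers to a website for that brush's instructions. Pressure variability in the two arms cannot be compared from this document.
- **That power falls by some amount.** The planning inputs in section 11.8 (difference 0.67, standard deviation 0.84) say nothing about pressure. Any variance increase would be invented, so no power figure should be given.

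**Conclusion.** The contradiction is real and narrow. For one placement of one brush, section 8.3 and step 5 of Appendix 2 give different pressure instructions; both apply to the sonic arm, and no text says which governs. It deserves correction because the protocol itself ties force to recession, a component of the primary score, and because nothing scheduled would show which instruction was followed. It reaches all 30 sonic-arm patients as wording. The size and direction of any effect on the abrasion score cannot be stated.

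This assumes that patients receive the manual substantially as printed in Appendix 2, as section 6.3 implies. If the site already hands out a single reconciled technique sheet, the fault is only in the protocol text.

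**What to change.** The sponsor should reconcile the pressure wording of section 8.3 with step 5 of Appendix 2 and give sonic-arm patients one consistent brushing-technique statement. Sections 6.3 and 6.6 should then say which technique text governs during the study. What the pressure instruction should say is for the sponsor to decide.

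The precedence statement should be limited to brushing technique. Appendix 2 also carries the device warnings and cautions, and section 15.7 makes the instructions for use stand in for the investigator's brochure, so the leaflet's safety cautions should be expressly kept in force.

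The cost is one patient-facing technique statement and matching wording in three sections, handled under section 15.2 if the protocol is already approved. Sample size, visits and analysis are unaffected.
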